## 17. DIGITAL ASSESSMENTS

Vocal and/or behavioral digital assessments will be conducted with HIPAA compliant digital application that have been downloaded on the patient’s smartphone with an iOS or Android operating system. The applications will be used for active collection of brief vocal samples for subsequent analysis of acoustic features that are associated with affective states and for passive acquisition of metadata to assess behavioral pattern that are associated with affective or cognitive states. The data will be reported in a separate protocol.

## 18. PHARMACOKINETIC/PHARMACODYNAMIC ANALYSES

A summary table of concentrations by visit for patients randomized to BTRX-246040 including number of patients who are below the limit of quantification (BLQ) and will be presented. Pharmacokinetic data collected in this study will be listed for the Pharmacokinetic Analysis Set.

Population PK analysis of the plasma concentrations in this study will be reported separately.

Other exploratory analyses, such as the relationship between BTRX-246040 exposure and efficacy measures or AEs or other safety endpoints, may be undertaken as deemed appropriate.

---

Document:	C:\Users\q718413\Documents\NEP-MDD-201_SAP_v1.0_Final_06Dec2018.docx		
Author:	[name]	Version Number:	1.0
		Version Date:	06Dec2018

Template No: CS\_TP\_BS016 Revision 4  
Effective Date: 01Apr2016

Reference: CS\_WI\_BS005

## 19. PHARMACOGENETIC ANALYSIS

Information regarding the collection of pharmacogenetic sample will be listed. Any analysis of pharmacogenetic sample will be reported separately.

---

Document:	C:\Users\q718413\Documents\NEP-MDD-201_SAP_v1.0_Final_06Dec2018.docx		
Author:	[name]	Version Number:	1.0
		Version Date:	06Dec2018

Template No: CS\_TP\_BS016 Revision 4  
Effective Date: 01Apr2016

Reference: CS\_WI\_BS005

Copyright © 2009, 2010, 2012, 2016 Quintiles Transnational Corp. All rights reserved.  
The contents of this document are confidential and proprietary to Quintiles Transnational Corp. Unauthorized use, disclosure or reproduction is strictly prohibited.

## APPENDIX 1. PROGRAMMING CONVENTIONS FOR OUTPUTS

### IQVIA OUTPUT CONVENTIONS

Outputs will be presented according to IQVIA's Global Biostatistics Standard Output Conventions.

#### DATES & TIMES

Depending on data available, dates and times will take the form yyyy-mm-ddThh:mm:ss.

#### SPELLING FORMAT

English US.

#### PRESENTATION OF TREATMENT GROUPS

For outputs, treatment groups will be represented as follows and in that order:

- BTRX-246040
- Placebo

#### PRESENTATION OF VISITS

For outputs, visits will be represented as follows and in that order:

Long Name (default)	Short Name
Baseline	BL
Week 1	W1
Week 2	W2
Week 4	W4
Week 6	W6
Week 8	W8
Safety Follow Up	SFU

---

Document: C:\Users\q718413\Documents\NEP-MDD-201\_SAP\_v1.0\_Final\_06Dec2018.docx  
Author: [name]  
Version Number: 1.0  
Version Date: 06Dec2018

Template No: CS\_TP\_BS016 Revision 4  
Effective Date: 01Apr2016

Reference: CS\_WI\_BS005

Copyright © 2009, 2010, 2012, 2016 Quintiles Transnational Corp. All rights reserved.  
The contents of this document are confidential and proprietary to Quintiles Transnational Corp. Unauthorized use, disclosure or reproduction is strictly prohibited.

Analysis Plan

**LISTINGS**

All listings will be ordered by the following (unless otherwise indicated in the template):

- randomized treatment group, first by BTRX-246040 and then placebo,
- center-subject ID,
- date (where applicable),
- For listings where non-randomized patients are included, these will appear in a category after the randomized treatment groups labeled 'Not Randomized'.

**APPENDIX 2. PARTIAL DATE CONVENTIONS**

Imputed dates will NOT be presented in the listings.

**ALGORITHM FOR TREATMENT EMERGENCE OF ADVERSE EVENTS:**

START DATE	STOP DATE	ACTION
Known	Known	If start date < study med start date, then not TEAE If start date >= study med start date, then TEAE
	Partial	If start date < study med start date, then not TEAE If start date >= study med start date, then TEAE
	Missing	If start date < study med start date, then not TEAE If start date >= study med start date, then TEAE
Partial, but known components show that it cannot be on or after study med start date	Known	Not TEAE
	Partial	Not TEAE
	Missing	Not TEAE
Partial, could be on or after study med start date	Known	If stop date < study med start date, then not TEAE

Document: C:\Users\q718413\Documents\NEP-MDD-201\_SAP\_v1.0\_Final\_06Dec2018.docx  
 Author: [name]  
 Version Number: 1.0  
 Version Date: 06Dec2018

Template No: CS\_TP\_BS016 Revision 4  
 Effective Date: 01Apr2016  
 Reference: CS\_WI\_BS005

Copyright © 2009, 2010, 2012, 2016 Quintiles Transnational Corp. All rights reserved.  
 The contents of this document are confidential and proprietary to Quintiles Transnational Corp. Unauthorized use, disclosure or reproduction is strictly prohibited.

Analysis Plan

START DATE	STOP DATE	ACTION
		If stop date >= study med start date, then TEAE
	Partial	Impute stop date as latest possible date (i.e. last day of month if day unknown or 31st December if day and month are unknown), then: If stop date < study med start date, then not TEAE If stop date >= study med start date, then TEAE
	Missing	Assumed TEAE
Missing	Known	If stop date < study med start date, then not TEAE If stop date >= study med start date, then TEAE
	Partial	Impute stop date as latest possible date (i.e. last day of month if day unknown or 31st December if day and month are unknown), then: If stop date < study med start date, then not TEAE If stop date >= study med start date, then TEAE
	Missing	Assumed TEAE

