### 11.3.1 ADVERSE EVENTS

An AE is any sign, symptom, illness, clinically significant abnormal laboratory value or ECG finding, or other untoward medical occurrence associated with the use of an investigational product that appears or worsens in a subject during a clinical study. This definition does not imply a causal relationship between the AE and the investigational product.

Adverse events beginning with the initial dose of investigational product or during the subsequent duration of their enrollment in the study will be considered treatment-emergent AEs (TEAE). TEAEs will be recorded on the AE CRF to include the event, date of onset, whether the AE is associated with an episode of self-harm, severity, frequency, seriousness, date of resolution, action taken with respect to the AE (e.g., discontinue study drug, begin concomitant medication, begin non-pharmacological treatment, etc.), outcome, and relationship to the investigational product. All TEAEs related to study drug will be followed through resolution or 30 days after the patient terminates from the study, whichever occurs first.

Medical conditions present or AEs occurring prior to the first dose of investigational product will be captured as medical history in the CRF. Any AE occurring during the study that is related to a pre-existing condition or event that worsens in intensity or frequency after the first dose of investigational product will be recorded as a TEAE.

Lack of drug effect is not an AE in clinical studies because the purpose of the clinical study is to establish drug effect.

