## 12. CONCOMITANT ILLNESSES

Concomitant medical and psychiatric information will be presented for the SAF set. Concomitant illnesses are defined as those conditions which start prior to or at Screening and are ongoing at the date of screening. Concomitant illnesses will be coded using MedDRA version 20.0 and presented by treatment group, SOC and PT.

Information regarding all concomitant illnesses will be listed alongside information for historical medical and psychiatric conditions

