**16.1. ADVERSE EVENTS**

Adverse Events (AEs) will be coded using Medical Dictionary for Regulatory Activities (MedDRA) central coding dictionary, Version 20.0.

Treatment emergent adverse events (TEAEs) are defined as AEs that started or worsened in severity on or after the first dose of study medication.

See [APPENDIX 2](#) for handling of partial dates for AEs. In the case where it is not possible to define an AE as treatment emergent or not, the AE will be classified by the worst case; i.e. treatment emergent.

An overall summary of number of patients within each of the categories described in the sub-section below will be provided as specified in the templates.

Listings will include TEAEs and Non-TEAEs.

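### The SAP's treatment-emergence algorithm has no branch for worsening, so an event that began before the first dose and worsened on drug can be left out of the TEAE tables if its original onset date is kept

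*SAP*

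**What the plan says.** Three places bear on whether an event that predates treatment counts as treatment-emergent.

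- SAP 16.1 (Adverse Events) defines TEAEs as "AEs that started or worsened in severity on or after the first dose of study medication". It sends the reader to Appendix 2 "for handling of partial dates for AEs", and classes an event as treatment-emergent when its status cannot be established.
- Protocol 11.3.1 (Adverse Events) says that an AE linked to something already present "that worsens in intensity or frequency after the first dose of investigational product will be recorded as a TEAE". The same section says: "Medical conditions present or AEs occurring prior to the first dose of investigational product will be captured as medical history in the CRF". The AE CRF carries a date of onset.
- SAP Appendix 2 (Algorithm for Treatment Emergence of Adverse Events) says, for a known start date with a known, partial or missing stop date: "If start date < study med start date, then not TEAE". For a start date described as "Partial, but known components show that it cannot be on or after study med start date", the action is non-emergent for every state of the stop date.

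SAP 16.1.1 to 16.1.5 build their summaries from TEAEs. Non-TEAEs appear in listings. SAP 3.3 declares no departures from the protocol.

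**The concern.** The definition has two limbs, a new start or a worsening, and the algorithm implements only the first. A programmer who follows Appendix 2 line by line will class as non-emergent an event that SAP 16.1 and protocol 11.3.1 both call treatment-emergent. The SAP does not say which of its two rules governs.

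At stake are the by-arm summaries on which tolerability, a secondary objective, will be judged. A worsening classed as non-emergent leaves the incidence table and the severity and relationship breakdowns. It also leaves the tables of TEAEs leading to drug withdrawal, TEAEs leading to study discontinuation, serious TEAEs and TEAEs associated with self-harm. The rule is the same in both arms, but if the drug aggravates existing symptoms the omissions would fall mainly in the active arm.

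**Working it through.** There is no figure in the plan to reproduce; this is a check of logic.

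**Step 1. The algorithm as a rule.** From Appendix 2:

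- Start known: TEAE if and only if start ≥ first dose.
- Start partial and certainly pre-dose: not TEAE.
- Start partial and possibly on or after first dose, or start missing: TEAE if the stop date is missing, or if the stop date (taken at its latest possible value when partial) ≥ first dose; otherwise not TEAE.

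**Step 2. Run over all states.** The first dose was set at 15 March 2018 for illustration. Six start-date states were crossed with four stop-date states (known before dose, known after dose, partial and ambiguous, missing), giving 6 × 4 = 24 combinations. A few cannot occur in real data because the stop precedes the start; they do not affect the result.

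| Start date | Classed TEAE, of 4 stop states |
|---|---|
| Known, before first dose | 0 |
| Known, day of first dose | 4 |
| Known, after first dose | 4 |
| Partial, certainly before first dose | 0 |
| Partial, ambiguous | 3 (all but a known pre-dose stop) |
| Missing | 3 (all but a known pre-dose stop) |

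No combination consults severity or frequency. A pre-dose start is non-emergent in 8 of 8 cases, even when the event is ongoing.

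**Step 3. One worsening, recorded two ways.** Onset 1 March, first dose 15 March, worsening 1 April, ongoing.

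- Original onset kept (start = 1 March): 1 March < 15 March, so not TEAE. This contradicts SAP 16.1 and protocol 11.3.1.
- New record dated at the worsening (start = 1 April): 1 April ≥ 15 March, so TEAE. This agrees with both.

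**Step 4. Does another provision rescue the first case?**

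- The worst-case rule in SAP 16.1 applies only when status cannot be established. With a known pre-dose start, Appendix 2 leaves nothing undetermined.
- SAP 16.1 cites the appendix for partial dates, but the appendix's first three rows rule on fully known start dates, so the table reaches every AE.
- Protocol 11.3.1 asks for a date of onset without saying whether, for a worsening, that is the original onset or the day of worsening.

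**Step 5. A second mismatch.** The SAP counts worsening in severity. The protocol counts worsening in intensity or frequency. An event that becomes more frequent without becoming more severe meets the protocol's rule but not the SAP's.

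**The case against.** The strongest reply is that the protocol leans towards the harmless way of recording. Its AE definition covers something that appears or worsens, it sends the pre-dose condition to medical history, and it has the worsening entered on the AE CRF. With two separate records, the natural onset of the second is the day of worsening, and the algorithm then counts it. This stands as far as it goes: the loss is conditional. It does not remove the contradiction, because neither document states the convention and keeping the original onset is a foreseeable choice at a site.

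A reader might infer that, since pre-dose events belong in medical history, any AE-page record with a pre-dose start must be a worsening, so that the rule removes only worsenings. The documents do not support this. AE review at Visit 2 comes before the first dose (protocol 9.2). Under protocol 11.3.4 a pre-dose SAE attributed to a protocol procedure is reportable, and SAEs also go on the AE CRF. SAP 16.1 itself expects non-TEAEs in the listings. The pre-dose branch therefore has a legitimate use.

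A reader might also want to size the loss from the insomnia counts in the earlier MDD study (7/69 against 0/65, protocol section 5). Nothing says that any of those cases was a worsening of a pre-dose complaint, so any figure would only restate an assumed share, which could be anything from none to all.

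Finally, affected events stay in the listings, and SAP 16 plans no statistical comparison of safety data by default. Both points are correct and limit the severity. The descriptive TEAE counts are nonetheless the main by-arm safety summary.

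**Conclusion.** The point holds in conditional form. Appendix 2 as written conflicts with the SAP's own TEAE definition and with the protocol's worsening rule, and nothing else in either document resolves the conflict. Events can be lost from the TEAE tables only where the AE record keeps a pre-dose onset date. Where the worsening is a new record dated at the worsening, the effect is nil. The documents do not allow the loss to be quantified, and they do not support saying that worsenings will drop out as a matter of course.

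It deserves correction because a stated rule gives the wrong class under a foreseeable way of recording, and the repair is cheap.

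A neighbouring gap is separate and minor: a condition that begins between screening and first dose fits neither the history definition in SAP 11 (stopped by screening) nor the concomitant-illness definition in SAP 12, "those conditions which start prior to or at Screening and are ongoing at the date of screening". It has no bearing on TEAE status.

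**What to change.** Do one or both of the following.

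1. In Appendix 2, for start dates that are known or certainly pre-dose, replace the present action with: not TEAE if the event stopped before first dose; TEAE if it worsened in severity or frequency on or after first dose; otherwise not TEAE. The stop-date test comes first so that events resolved before dosing are not pulled in.
2. State in the SAP and the CRF completion instructions that a worsening is entered as a new AE record whose start date is the date of worsening. The existing date logic then gives the right class.

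In either case, align the worsening criterion in SAP 16.1 with the intensity-or-frequency wording of protocol 11.3.1.

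Before unblinding, list the AE-page records that have a pre-dose start and no pre-dose stop. If there are none, the matter is closed in practice; if there are some, each can be resolved blind.

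The cost is a few lines of SAP text and a small derivation change, and possibly a few more events counted as treatment-emergent in both arms. Option 1 needs a way to identify worsening. The AE CRF items listed in protocol 11.3.1 include severity and frequency but no worsening flag or pre-dose grade, so option 2 is simpler where records can still be entered or queried that way.

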**ALGORITHM FOR PRIOR / CONCOMITANT MEDICATIONS:**

START DATE	STOP DATE	ACTION
Known	Known	If stop date < study med start date, assign as prior If stop date >= study med start date, assign as concomitant
	Partial	Impute stop date as latest possible date (i.e. last day of month if day unknown or 31 st December if day and month are unknown), then: If stop date < study med start date, assign as prior If stop date >= study med start date, assign as concomitant
	Missing	If stop date is missing could never be assumed a prior medication If start date <= end of treatment, assign as concomitant
Partial	Known	Impute start date as earliest possible date (i.e. first day of month if day unknown or 1 st January if day and month are unknown), then: If stop date < study med start date, assign as prior If stop date >= study med start date, assign as concomitant

Document: C:\Users\q718413\Documents\NEP-MDD-201\_SAP\_v1.0\_Final\_06Dec2018.docx  
 Author: [name]  
 Version Number: 1.0  
 Version Date: 06Dec2018

Template No: CS\_TP\_BS016 Revision 4  
 Effective Date: 01Apr2016  
 Reference: CS\_WI\_BS005

Copyright © 2009, 2010, 2012, 2016 Quintiles Transnational Corp. All rights reserved.  
 The contents of this document are confidential and proprietary to Quintiles Transnational Corp. Unauthorized use, disclosure or reproduction is strictly prohibited.

Analysis Plan

START DATE	STOP DATE	ACTION
	Partial	Impute start date as earliest possible date (i.e. first day of month if day unknown or 1 st January if day and month are unknown) and impute stop date as latest possible date (i.e. last day of month if day unknown or 31 st December if day and month are unknown), then: If stop date < study med start date, assign as prior If stop date >= study med start date, assign as concomitant
	Missing	Impute start date as earliest possible date (i.e. first day of month if day unknown or 1 st January if day and month are unknown), then: If stop date is missing could never be assumed a prior medication If start date <= end of treatment, assign as concomitant
Missing	Known	If stop date < study med start date, assign as prior If stop date >= study med start date, assign as concomitant
	Partial	Impute stop date as latest possible date (i.e. last day of month if day unknown or 31 st December if day and month are unknown), then: If stop date < study med start date, assign as prior If stop date >= study med start date, assign as concomitant
	Missing	Assign as concomitant

---

Document: C:\Users\q718413\Documents\NEP-MDD-201\_SAP\_v1.0\_Final\_06Dec2018.docx  
 Author: [name]  
 Version Number: 1.0  
 Version Date: 06Dec2018

Template No: CS\_TP\_BS016 Revision 4  
 Effective Date: 01Apr2016  
 Reference: CS\_WI\_BS005

Copyright © 2009, 2010, 2012, 2016 Quintiles Transnational Corp. All rights reserved.  
 The contents of this document are confidential and proprietary to Quintiles Transnational Corp. Unauthorized use, disclosure or reproduction is strictly prohibited.
